Hypothesis 1: Greater CB WML volume is associated with a) reduced resting-state connectivity of frontal, temporal, and cingulate regions and b) deficits in attention, memory and processing speed.

Hypothesis 2: Greater UF WML volume is associated with a) reduced resting state functional connectivity between frontocingulate and medial temporal regions, and b) greater depression severity and negativity bias.

Exploratory Hypothesis: Greater CB WML volume is associated with failure of anterior and posterior DMN nodes to deactivate during attentional components of the fMRI task. Greater UF WML volume is associated with greater medial temporal reactivity during affective components of the fMRI task.

Specific Aim 2: To determine whether deficits in tract structural / functional connectivity predict nonremission to antidepressant treatments and if these relationships vary based on antidepressant mechanism of action.

Hypothesis 3: Nonremission to escitalopram will be predicted by: a) greater WML volume in the CB and UF, and b) reduced resting functional connectivity between structures connected by the CB and UF. Greater WML severity and reduced functional connectivity in these tracts will not significantly predict response to placebo.

Hypothesis 4: Nonremission to bupropion will be predicted by a) greater WML volume in the UF but not CB, and b) reduced resting functional connectivity deficits between structures connected by the UF but not CB.

Exploratory Aims: **Expl. Aim 1)** To determine if specific cognitive measures may serve as markers of focal tract WML damage. **Expl. Aim 2)** To use whole-brain multimodal imaging approaches to examine how connectivity differences in other brain regions may also predict nonremission to antidepressants.

For exploratory analyses, we will also recruit 30 elders with no psychiatric history. Data from this population will help us understand whether our neural and cognitive findings in depression represent differences from what is seen in healthy aging, or whether our observations in depressed elders are within the range of normal aging. This will be important for data interpretation and planning for future projects.

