4.0 ENTRY CRITERIA

We plan to enroll a cohort of 200 individuals to meet goals of having 130 evaluable subjects. Participants will meet DSM-IV-TR criteria for MDD, single episode, recurrent, or chronic. We will not be enrolling vulnerable populations, specifically pregnant women, children, prisoners, or institutionalized individuals. We also will not enroll subjects incapable of providing their own consent. Should a potential subject present where there is a concern (either by a study clinician or staff member) about their ability to understand study procedures and provide meaningful consent, their cognitive ability and understanding will be evaluated by a study doctor. If there is any concern that the individual may be impaired, they will not be enrolled in the study. The rationale will be provided to the individual as well as his or her family members. Referrals for further evaluation, including urgent or emergent evaluation, will be made as needed and clinically warranted.

Men and women of all races / ethnicities are eligible.

Depressed Cohort:

Inclusion Criteria:

- 1) Age 60 years or older.
- 2) Current diagnosis of major depressive disorder (DSM-IV-TR), single episode, recurrent or chronic, without psychotic features, as detected by MINI and clinical exam.
- 3) Minimum MADRS score ≥ 15 .
- 4) Mini-Mental State Exam ≥ 24 .
- 5) Fluent in English.

Exclusion Criteria:

Diagnostic Issues:

- 1) Current or past diagnoses of other Axis I psychiatric disorders, except for generalized anxiety disorder (GAD) symptoms occurring during a depressive episode
- 2) History of alcohol or drug dependence or abuse in the last three years
- 3) History of developmental disorder or IQ score < 70
- 4) Presence of acute suicidal ideation, defined as a "yes" response to items 3, 4, or 5 on the C-SSRS
- 5) Acute grief (< 1 month)

Protocol Version: 2.0

Protocol Date: 04/10/2020

- 6) Current or past psychosis

Medical Issues:

- 7) Primary neurological disorder, including but not limited to dementia, stroke, brain tumors, epilepsy, Parkinson's disease, or demyelinating diseases
- 8) MRI contraindications
- 9) Any physical or intellectual disability adversely affecting ability to complete assessments
- 10) Current pregnancy or capable of becoming pregnant (defined as ability to have children [i.e., has not had a hysterectomy or bilateral oophorectomy] and is not clearly postmenopausal [> 1 year of amenorrhea])

Antidepressant Treatment Issues:

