9.0. RANDOMIZATION & STUDY DRUG ADMINISTRATION

9.1. Randomization: After initial assessments, participants are randomized to double-blinded Phase 1 drug assignment (escitalopram or placebo). As our primary interest for Phase 1 is related to escitalopram response, we will allocate participants in a 2:1 drug-to-placebo ratio. Randomization will be conducted by the Vanderbilt Investigational Drug Service. Nondepressed individuals will not be randomized to study drug.

Randomization will be stratified by MRI measures of total cerebral WML volume. Our measurement of total WML volume is automated and available within 24 hours of the scan and subjects will be stratified as "high" or "low" total cerebral WML volume. Based on pilot data, we will use a cutoff of 3.86mL; this is the median 3T WML volume from a cohort of 145 depressed elders analyzed using our WML segmentation method. When we reach 50% enrollment, we will re-assess this cutoff based on study data and adjust if necessary.

If there are delays in scan processing, stratification will be determined using the Coffey-modified Fazekas visual rating scale (2), dichotomizing participants as "high" (2 or 3, confluence of foci) or "low" (0 or 1, absent or punctate foci).

MRI measures will only be used for stratification. They will not guide or determine treatment decisions.

9.2. Phase 1: Blinded Escitalopram or Placebo: We selected escitalopram due to its tolerability, ease of dosing, and lack of effects on dopamine and norepinephrine (115). The Vanderbilt IDS will prepare over-encapsulated escitalopram and matching placebo and maintain the blinded assignment in case of emergencies. Participants will receive one tablet (10mg or placebo) for at least 2 weeks. If tolerated, it can be increased to a target dose of two tablets (20mg) daily at the two-week study contact, but dosing changes will not be made at week 6 or later. For problems with tolerability, the dose can be reduced to the previous level, but not below one tablet daily.

9.3. Transition: After 8 weeks subjects will be assessed for remission (MADRS \leq 7). Those achieving remission will end their study participation. Those who are not remitted will have their Phase 1 drug tapered over a week to decrease the chance of discontinuation syndrome then progress to Phase 2.

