We will use a similar approach for Exploratory Aim 1, where we examine how cognitive test performance may serve as a marker of WML tract damage. Including the previous covariates plus education, cognitive test results will be on the independent side with tract WML values on the dependent side.

Data from nondepressed elders will be integrated into the above analyses. We will test for group differences in the neuroimaging and cognitive measures described above. We will also include a group variable (depressed or not depressed) in analyses.

Aim 2 examines how tract measures predict remission. Following our previous approach (21), our definition of remission is MADRS ≤ 7 . Secondly, we will examine drug response (50% improvement on MADRS). Remission / response status for subjects with missing data will be estimated via multiple imputation

method assuming that dropouts are missing at random.

We will use two regression models to test for mediation while adjusting for baseline MADRS, age, sex, and vascular risk. To assess indirect effects of tract WML and FC measures as mediator variables, we will regress a potential mediator on a tract-based measure (an explanatory variable of interest). We will fit another model in which antidepressant remission or nonremission serves as outcome variable, and the potential mediator and tract-derived measure serve as covariates. The second model can be either logistic or linear regression model depending on the nature of outcome. The product of two beta coefficients corresponding to the tract-based measure in the first model and to the mediation variable in the second model will be assessed by constructing bootstrapped 95% confidence intervals (CI); statistically significant difference from zero implies that the relationship between the outcome and explanatory variable is mediated by the variable in question (127,128).

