This approach will slightly differ for each study phase. For Phase 1, models will include drug arm (placebo or escitalopram). To examine for differences in how tract impairment affects remission in each arm, we will test for interactions between drug assignment and tract integrity (WML & FC). We will explore significant interactions in individual models. For subjects entering Phase 2, we will test for differences in tract integrity (WML & FC) between those originally assigned to escitalopram and placebo. If differences are observed, in models we will control for original Phase 1 cohort assignment. In exploratory models, we will use similar approaches to test for the additional effect of cognitive domain function (Table 5) on remission. We will also use this approach for Exploratory Aim 2 when we examine the effect of connectivity deficits in other tracts.

Importantly, the relationship between connectivity and antidepressant response may not be linear. It is possible that a ‘threshold’ must be crossed in order for tract connectivity deficits to influence response (3). To properly take into account nonlinear effect of a continuous predictor variable (e.g., WML, FC) on response variable (e.g., remission or nonremission) in the models, we will employ restricted cubic splines of the predictor. Statistical significance of the nonlinear terms via F-test implies that the relationship between the two measures of interest can be nonlinear.

15.1. Sample Size and Statistical Power:

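### Phase 2 models adjust for Phase 1 arm only if a weak, undefined pre-test finds a tract difference; the resulting bias is small, and always adjusting would remove it

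*Combined protocol and SAP*

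**What the plan says.** Section 15.0 treats the two phases differently. In Phase 1, arm is always in the model: "For Phase 1, models will include drug arm (placebo or escitalopram"). In Phase 2 there is a preliminary step, "For subjects entering Phase 2, we will test for differences in tract integrity (WML & FC) between those originally assigned to escitalopram and placebo", and then the conditional rule, "If differences are observed, in models we will control for original Phase 1 cohort assignment". The standing Aim 2 adjustment is described as "adjusting for baseline MADRS, age, sex, and vascular risk"; Phase 1 arm is not in that list, and no other section makes it unconditional for Phase 2.

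Entry to Phase 2 is mainly by nonremission in either arm (sections 7.0 and 9.3). Section 14.0 also allows early transfer for worsening depression or intolerable adverse events. Hypothesis 3 in section 2.0 states that "Nonremission to escitalopram will be predicted by: a) greater WML volume in the CB and UF", and that tract damage will not significantly predict response to placebo.

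**The concern.** A covariate confounds the tract coefficient when it relates both to the tract measure and to the outcome. Prior arm may do both in Phase 2.

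- **Arm and tract.** If Hypothesis 3 is true, failing escitalopram selects for cingulum bundle (CB) and uncinate fasciculus (UF) damage, and failing placebo does not. The section 9.1 rule, "Randomization will be stratified by MRI measures of total cerebral WML volume", balances total lesion volume at randomization. It cannot prevent selection that happens eight weeks later.
- **Arm and bupropion outcome.** One group has just failed an active study drug and is tapered from it; the other has not. Early transfer may also differ by arm. The pre-test does not look at this link at all.

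The pre-test is also undefined. The text does not say what counts as a difference, which measure (CB or UF, lesion volume or connectivity) triggers adjustment, or whether a trigger applies to every model. Hypothesis 4 is a contrast, UF but not CB, so a measure-by-measure reading could give the two models different covariates. At stake is the accuracy of the Phase 2 tract coefficients on which Hypothesis 4 rests.

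**Working it through.** The plan gives no Phase 2 sample size, power or pre-test threshold (section 15.1 powers Phase 1), so there is no figure to reproduce.

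**Inputs from the documents.** 130 evaluable (section 4.0, "to meet goals of having 130 evaluable subjects"); 2:1 allocation (section 9.1, "we will allocate participants in a 2:1 drug-to-placebo ratio"), so about 87 and 43; base nonremission 0.36 and detectable log ratio 0.45 (section 15.1).

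**Assumptions.** Nonremission by arm is not given: 36–64% (escitalopram) and 36–75% (placebo) are used. The 0.45 is read as a log odds ratio per SD; 0.80 is a stronger case. Pre-test: two-sided t-test on one measure at 0.05. Phase 2 base nonremission 55%. Odds ratio for prior arm on bupropion nonremission: 1 to 5.

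**Step 1, Phase 2 size.** At 36% in both arms: 87 × 0.36 ≈ 31 and 43 × 0.36 ≈ 15, total 46. At 64% and 75%: 56 + 32 = 88.

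**Step 2, imbalance implied by Hypothesis 3.** With slope β and nonremission rate q, the mean tract shift in escitalopram nonremitters is roughly β(1 − q) SD; in placebo nonremitters it is 0.
- β = 0.45: 0.45 × 0.64 = 0.29 down to 0.45 × 0.36 = 0.16 (exact: 0.28 to 0.16).
- β = 0.80: 0.80 × 0.64 = 0.51 down to 0.80 × 0.36 = 0.29 (exact: 0.45 to 0.26).

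**Step 3, power of the pre-test** (noncentral t). From 31 + 15 to 56 + 32 entrants, power is 15–27% for a difference of 0.3 SD and 34–61% for 0.5 SD; 80% power needs about 0.88 to 0.62 SD. In simulated trials the pre-test fired in 11–19% at β = 0.45 and 25–42% at β = 0.80.

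**Step 4, bias if arm is omitted.** Approximately ln(OR) × d × p(1 − p), where d is the tract difference and p the escitalopram-first share. With 31 of 59 entrants, d = 0.45 and OR 5: 1.609 × 0.45 × 0.249 = 0.18. Simulation gave 0.179.

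**Step 5, bias under the plan's rule.** Simulated median tract log odds ratio per SD, true value 0:

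| β; nonremission (escitalopram/placebo); entrants | Arm OR | Arm never in | Plan's rule | Arm always in | Type I error, plan's rule |
|---|---|---|---|---|---|
| 0.45; 60/70%; 82 | 2 | 0.018 | 0.010 | -0.008 | 4.7% |
| | 3 | 0.048 | 0.034 | 0.001 | 3.9% |
| | 5 | 0.071 | 0.051 | 0.007 | 4.4% |
| 0.80; 60/70%; 82 | 2 | 0.055 | 0.031 | 0.007 | 4.8% |
| | 3 | 0.077 | 0.038 | -0.004 | 4.3% |
| | 5 | 0.113 | 0.061 | -0.004 | 5.0% |
| 0.80; 36/64%; 59 | 2 | 0.088 | 0.034 | -0.002 | 4.8% |
| | 3 | 0.132 | 0.060 | 0.014 | 4.4% |
| | 5 | 0.179 | 0.075 | 0.005 | 4.4% |

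With 36% in both arms (46 entrants), the top of the plan's-rule column rises to about 0.10. Standard errors run from about 0.25 to 0.35, so the largest bias is roughly 0.10 / 0.35 ≈ 0.3 of a standard error. Across reruns, type I error under the plan's rule was 3.7–5.6%. With an arm odds ratio of 1 there is essentially no bias.

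**Step 6, cost of always adjusting.** With a true tract log odds ratio of 0.45, arm OR 2 and β = 0.45, the plan's rule estimates 0.484–0.488 with power 34–46%; always adjusting estimates 0.472–0.477 with power 31–43%.

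**The case against.** The plan saw the selection problem and wrote a rule for it, and that rule does most harm-reduction where it matters: it tends to fire when the imbalance is large. Several further points stand.

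- **False findings.** A reader might infer that leaving arm out will create false CB or UF associations. The numbers do not support that. Rejection under the plan's rule stays near 5%, and the bias is well inside sampling error.
- **Accuracy.** Root-mean-square error is equal or slightly lower under the plan's rule (0.26–0.28 against 0.27–0.29 when arm is always included, at 50% and 65% nonremission). Always adjusting trades a little variance for the removal of bias; it does not buy overall accuracy.
- **The trigger may be broader than one test.** The plan compares several measures. If any of four (assumed correlation 0.4) can trigger adjustment, the firing rate rises from 12–42% to 24–52%. So at strong Hypothesis 3 effects arm would be included about half the time, and it is too strong to say that it would nearly always be left out.
- **The arm effect on bupropion outcome is assumed.** The documents give no size. Section 9.7 also softens the contrast: people entering through washout have already failed an adequate antidepressant course, so some placebo-first entrants have failed an active drug too.
- **No tract difference, no confounding.** If tract measures truly do not differ by arm, omitting arm loses a prognostic covariate but does not confound the tract coefficient.

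None of this is a reason to keep the pre-test. It has low power at the imbalance the study predicts, it examines only one of the two links that make a confounder, and it leaves a covariate choice open until the data are seen.

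**Conclusion.** The point holds as a modest weakness in the Phase 2 analysis. The conditional rule is in the current text, it is undefined, and on a single-measure reading it misses the imbalance predicted by Hypothesis 3 in most scenarios. If prior arm also affects bupropion outcome with an odds ratio of 2 to 5, the tract coefficients carry a residual bias of about 0.02 to 0.10 log odds ratio per SD (nearer 0.01 in the mildest case), well under one standard error.

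This rests on assumed nonremission rates by arm, an assumed arm effect and an assumed 0.05 trigger. It does not show an inflated false-positive rate or that any Hypothesis 4 conclusion would change. Nor does adjustment undo the narrowing of tract range by Phase 1 selection: at slopes of 0.4 to 1.0 the escitalopram-first group keeps about 81–95% of the variance, with or without arm in the model.

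**What to change.** In section 15.0, replace the test-then-adjust sentences with: *All Phase 2 models include Phase 1 assignment as a covariate, whatever the observed difference in tract measures.* This matches the plan's own Phase 1 practice and gives the CB and UF models the same covariates.

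Cost: one degree of freedom, a standard error larger by about 3–8% in most scenarios, and about 3 points of power (part of that gap is the bias itself). No new data are needed and nothing in treatment changes.

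Optionally, report the CB and UF coefficients by Phase 1 arm as descriptive only. State that the placebo-first group is small (about 15 to 32 entrants over the assumed range) and that neither this table nor the covariate reverses Phase 1 selection on tract range.

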15.0 STATISTICAL CONSIDERATIONS

For **Aim 1**, inter-correlation matrices and scatter plots will be used to assess and visualize the patterns of association among the tract WML values and respective fMRI connectivity values. Multivariate analysis will be conducted using canonical correlation. Canonical correlation can accommodate more than one variable on both the independent and dependent sides of the general linear modeling equation and those variables may be either metric or nonmetric. In canonical analysis, the solution depends both on correlations among the variables in each set and on correlations among variables between sets. In a simultaneous process, underlying canonical variates (or factor loadings) comprising the WML values on the independent side will be constructed in such a way to maximize the correlations with canonical variates of the fMRI values on the dependent side. The same assumptions as those underlying multiple linear regression apply. Evaluations of normality, linearity, and homoscedasticity will be conducted, as will tests of multicollinearity and singularity of the underlying correlation matrices. Simple bivariate correlations and scatterplots will assist with describing and visually the patterns of association, canonical correlation will control for the inter-correlations among the WML and fMRI values will maximizing the correlation between the two sets. Covariates of *age, sex, and vascular risk* will be included with the WML measures. Effects of *MADRS and total brain WML volume* will also be examined. We will use a similar approach to examine how WML values are associated with clinical presentation. For Hypothesis 1, attention, memory, and processing speed scores will be on the dependent side. For Hyp. 2, BRISC and baseline MADRS scores will be on the dependent side.

For the fMRI emotional dot-probe task, we will examine how WMLs are associated with ROI activation(Exploratory Hyp). Specifically, we will examine how CB measures are associated with activity in DMN and CCN regions during the task's attentional component and how UF measures are associated with amygdala activity during the affective component. In this analysis WML measures will be on the "independent" side of the canonical correlation while fMRI activation values will be "dependent" side.

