Aim 1: From our published report (129) correlations of the FC of the PFC with the amygdala and the hippocampus were in the range of 0.52 to 0.55. A sample of 130 subjects, will have > 90% statistical power for associations ≥ 0.30 (two-tailed $\alpha = 0.05$). However, our primary approach to the analysis of Aim 1 will use canonical correlation with no known powering algorithms; sample size and effect estimates are used to guide the appropriateness. Using the multiple regression approach (single dependent) as a conservative estimate, a sample size of 130 achieves 83% statistical power to detect an R^2 as small as 0.06 (standardized beta = 0.20, 6% shared variance) attributed to the association of WML with a significance level (alpha) of 0.05 after adjusting for other proposed covariates. These calculations assume that the variables for which we are adjusting have an R^2 of 0.10 (10%) (130). We suspect that the control variables will have a higher inter-correlation value, thus increasing our power for testing the effect of a single variable.

Aim 2: The study includes a placebo arm to identify effects specific to an active depressant while having a comparable number of subjects receiving each active drug. Powering the study for Phase 1, Table 2 presents estimates for our proposed sample size using unadjusted effects of low vs. high WML values on the respective

outcomes of interest found in our preliminary data. The logistic regression approach allows for the testing of effects adjusted for known covariates. Using this approach, assuming a base non-remittance rate of 0.36 (36%), a sample size of 130 will enable us to detect a log hazard ratio as small as 0.45 for a specific measure. We conservatively included an assumption that covariates would account to up to 10% share of the effect on nonremission. If that value is less, our statistical power will increase for the same hazard ratio. Using high vs. low tract WML volume as an example, after controlling for other effects, our sample will enable us to detect an effect on the likelihood of non-remittance of at least 25% (high WML vs. low WML, $0.45 / 0.36 = 1.25$ or 25% increase). Continuous as well as nonlinear operationalization of effects will be examined.

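### The 83% power for Aim 1 is for one WML measure and one outcome; it is not a conservative bound for the planned canonical correlation

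*Combined protocol and SAP*

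**What the plan says.** Section 15.0 sets the Aim 1 method: "Multivariate analysis will be conducted using canonical correlation". WML values go on the independent side, with age, sex and vascular risk added there. The dependent side holds fMRI connectivity values, three cognitive scores for the clinical part of Hypothesis 1, or two clinical scores for Hypothesis 2.

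Section 15.1 says that no powering algorithm is known for this primary approach and offers a substitute: "Using the multiple regression approach (single dependent) as a conservative estimate, a sample size of 130 achieves 83% statistical power". The effect behind that figure is an R-squared of 0.06 for WML, with a beta of 0.20 given in brackets, tested at alpha 0.05 with the other covariates in the model. Those covariates are taken to have an R-squared of 0.10. The paragraph ends: "We suspect that the control variables will have a higher inter-correlation value, thus increasing our power for testing the effect of a single variable".

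The plan gives no reason why the single-outcome figure should be conservative. It does not state the number of WML or connectivity variables in a canonical set, the correlation among outcomes, or the multivariate test statistic.

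**The concern.** A conservative estimate should be a figure that the real analysis can be expected to meet or exceed. A test of one WML measure on one outcome uses one degree of freedom. An overall test of p WML measures against q outcomes uses p × q. If the effect is confined to one pair, the extra degrees of freedom cost power. If outcomes share the effect, or are correlated in a helpful way, the multivariate test can gain. Nothing in the plan shows which case applies.

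The risk lies in interpretation. A null canonical result might be read as evidence against an association because the study claimed 83% power, when the test actually run had much less for that effect.

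**Working it through.** **Inputs from Sections 15.0 and 15.1.** n = 130; R-squared for WML 0.06; covariate R-squared 0.10; alpha 0.05; three covariates; two or three clinical outcomes. The bracketed beta of 0.20 would give 0.20² = 0.04 for an uncorrelated predictor. I use 0.06, because that value reproduces the plan's power.

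**Assumptions, not in the documents.** One to four WML measures; equal outcome correlation ρ from 0 to 0.8; covariates partialled out; Wilks test.

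**Step 1: reproduce the 83%.** F test of an R-squared increment, noncentrality λ = n·f².
- f² = 0.06/0.90: power 0.832.
- f² = 0.06/(1 − 0.06 − 0.10) = 0.06/0.84: power 0.856.
- f² = 0.06/0.94: power 0.816.
- Two numerator degrees of freedom, with residual variance 0.84 or 0.94: 0.774 or 0.723. Three: 0.711 or 0.656.

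Only the one-degree-of-freedom test matches the plan.

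**Step 2: one WML measure, q outcomes.** The exact test is F(q, 130 − 3 − 1 − q), with λ = 130 × (0.06/0.90) × m = 8.67·m.
- All outcomes equally affected: m = q / [1 + (q − 1)ρ].
- One outcome affected: m = [1 + (q − 2)ρ] / [(1 − ρ)(1 + (q − 1)ρ)].

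For example, with q = 3 and ρ = 0.5, m = 3/2 = 1.5 in the first case and 1.5/(0.5 × 2) = 1.5 in the second. Then λ = 13.0 and power is 86% in both.

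| Outcomes | Affected | ρ = 0 | ρ = 0.5 | ρ = 0.6 | ρ = 0.8 |
|---|---|---|---|---|---|
| 2 | one | 74% | 86% | 91% | over 99% |
| 3 | one | 68% | 86% | 92% | over 99% |
| 2 | both | 97% | 86% | 84% | 79% |
| 3 | all | 99% | 86% | 82% | 74-75% |

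**Step 3: several WML measures, one of which carries the effect.** Simulated Wilks lambda with Rao's F, 4,000 runs per setting, null rejection 4.4-4.6%. Ranges reflect the choice of residual variance in Step 1.
- One affected pair, uncorrelated outcomes: about 52-64% for two WML measures with two or three outcomes.
- All outcomes affected, ρ = 0.5: about 73-78% for two WML measures and three outcomes (2 × 3), and about 56-64% for four and three (4 × 3).

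A shared effect does not always fall short with several measures. With three uncorrelated outcomes, m = 3 and λ = 26.0, which more than offsets the added degrees of freedom.

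**Step 4: the closing sentence on control variables.** Hold the WML increment at 0.06 and take f² = 0.06/(1 − R²) for the covariates. Raising the covariate R-squared from 0.10 to 0.20 to 0.30 moves power from 83% to 87% to 91%.

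**The case against.** The best defence is that the hypotheses expect several outcomes to be affected together. Hypothesis 1 names attention, memory and processing speed; Hypothesis 2 names depression severity and negativity bias. Each names the WML volume of one tract. With one WML measure, all outcomes affected and correlation at or below 0.5, power is 86-99%, and 83% is then indeed conservative. This stands. It rules out saying that the label always errs in one direction, but it does not rescue the label: Section 15.0 speaks of WML values in the plural, and no set size or correlation is fixed.

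The plan also says openly that it has no power method for canonical correlation. That is fair disclosure, but the Wilks test can be simulated, so it does not justify the substitute.

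A reader might infer several stronger points that the documents do not support.
- That the canonical test has less power unless several outcomes share the effect. Sharing is not necessary: one affected outcome at correlation 0.5 already gives 86%. Nor is it sufficient: three outcomes, all affected, at correlation 0.8 give 74-75%.
- That power is as low as the four-measure case suggests. Four is an assumption. Table 2 lists only three cingulum rows and is introduced under Aim 2.
- That the sentence ending "thus increasing our power for testing the effect of a single variable" is backwards. If covariates explain WML and the slope is held at 0.25, power does fall, from about 87% to 74% as they explain 0 to 30% of WML. But the increment then shrinks from 0.25² = 0.0625 to 0.0625 × 0.7 = 0.044, a different target. With the increment fixed, as the plan has it, the sentence can be right (Step 4).

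**Conclusion.** The description of the 83% as conservative is wrong as written. The arithmetic behind the 83% is sound for one WML measure and one outcome. It is not a lower bound for the primary canonical analysis: at the same effect, power ranges from about 52-64% (two WML measures, one affected pair, uncorrelated outcomes) to 99% (one measure, three uncorrelated outcomes, all affected). These figures rest on assumed set sizes, equal outcome correlations of 0 to 0.8, covariates partialled out and a Wilks test. They show that the claim is not established; they do not show that the planned test is underpowered. This is a correction to the justification and does not by itself call for a larger sample.

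**What to change.** In Section 15.1, remove the word conservative and label the 83% as the power for a single WML measure and a single outcome. State how many WML measures and outcomes enter each Aim 1 canonical analysis and name the test statistic. Report its power by simulation at R-squared 0.06 and n = 130, over a range of outcome correlations, for an effect in one outcome and for a shared effect.

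The closing sentence on control variables can stay; at most, clarify that it refers to outcome variance explained by the covariates. Making a one-degree-of-freedom regression the primary test, with canonical correlation as a summary, is an option and not a required correction.

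The cost is a wording change and a short simulation, with no new participants or data. The drawback is that the stated power may become less favourable.
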